4.9. Pharmacokinetic/Pharmacodynamic Analyses

Pharmacokinetic/pharmacodynamics (PK/PD) analyses will be conducted by PK/PD group.

4.10. Safety Analyses

Safety measures will include AEs, vital signs, treatment exposure, adjudicated cardiovascular events, laboratory measures, and antibodies to LY3209590. Safety analysis will be reported for Safety Population and data measured while on treatment and after study drug discontinuation will be included.

4.10.1. Study Drug Exposure

Exposure in days in the study will be calculated for each patient and summarized by treatment group. The mean of exposure will be compared between treatment groups using 2-sample *t*-test. Exposure during the treatment period will be calculated from date of first study basal insulin dose collected in the electronic case report form [eCRF] to date of discontinuation from study treatment (i.e., the last dose date for insulin degludec, and last dose date + 7 days for LY3209590 to account for the weekly injection). The sum of exposure in total patient years will also be provided.

Frequency of subjects falling into the following different exposure ranges will also be summarized: >0 days, ≥ 7 days, ≥ 14 days, ≥ 30 days (1 month), ≥ 60 days (2 months), ≥ 90 days (3 months), ≥ 120 days (4 months), ≥ 183 days (6 months) days.

In addition, the duration of follow-up in days for each individual patient is calculated from the date of last dose of study drug for insulin degludec/last dose of study drug + 7 days for LY3209590 to the last study visit date. The duration of the follow-up in days will be summarized (n, mean, standard deviation, median, sum in total patient years, minimum and maximum) by treatment group.

The duration on study from date of first study drug to the last study visit date (including the follow-up visit) will also be summarized by treatment group, the following summary statistics will be provided: n, mean, standard deviation, median, sum in total patient years, minimum and maximum.

A by-patient listing of drug exposure data will be created to provide data for the CSR appendix of Compliance and/or Drug Concentration Data.

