#### **Study Period 2: Treatment Period**

##### **Randomization (Week 0 [Visit 3])**

Study participants who continue to be eligible for the study will be randomized to 1 of the treatment arms. All measures to be performed at Visit 3 (see Schedule of Activities, Section 2) should be done prior to injection of the study participant's assigned investigational product (IP) to ensure that appropriate baseline measurements are obtained. Urine and serum pregnancy tests will be done before IP administration. The study participant will begin IP, if the urine pregnancy test is negative. If the result of the serum pregnancy test is positive, the study participant will be discontinued from the study (see Section 8.2).

Study personnel will inject the first dose of IP at the study site. The PK samples and ECGs at randomization must be collected as described in the Schedule of Activities (Section 2).

Following randomization, study participants will participate in a 32-week treatment period. During Weeks 1 to 8, site personnel will administer IP, and study participants will receive education and training on how to self-administer IP. The training should include information on reconstitution of IP, appropriate injection site locations, injection technique, and the signs and

symptoms of local adverse reactions, should that occur. During Weeks 9 to 12, IP will be reconstituted and administered at the site by the study participant, under supervision of trained site personnel to assure that the study participant is capable of self-administration. During Weeks 13 to 31 IP will be self-administered by the study participant at home, or optionally can be administered once weekly by site personnel. Information on self-injection can be reviewed as necessary throughout the study.

LY3209590 will be administered as one of two dose individualization algorithms ([Appendix 7](#)).

Insulin degludec will be self-administered daily by study participants after a training and first administration under site personnel supervision on Day 1 according to a modified Riddle algorithm (Section [7.2.1.2](#)).

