Study participants who *discontinue IP for any reason and are unwilling to return for a safety follow-up* visit, will be asked to perform an early termination (ET) visit as their final study visit. At this visit, study participants will perform procedures listed in the Schedule of Activities (Section 2).

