### **8.3. Lost to Follow-Up**

A study participant will be considered lost to follow-up if he or she repeatedly fails to return for scheduled visits and is unable to be contacted by the study site. Site personnel are expected to make diligent attempts to contact study participants who fail to return for a scheduled visit or were otherwise unable to be followed up by the site.

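### SAP 4.10.1 sets no floor on LY3209590 follow-up time, so an LY participant last seen 0 to 6 days after a dose gets -7 to -1 days of follow-up

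*SAP*

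**What the plan says.** SAP 4.10.1 defines three durations.

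- **Exposure** runs from the first dose to discontinuation of study treatment. For degludec the end is "the last dose date for insulin degludec". For LY it is the "last dose date + 7 days for LY3209590 to account for the weekly injection".
- **Follow-up** for LY runs from the "last dose of study drug + 7 days for LY3209590 to the last study visit date". For degludec it starts at the last dose itself. The section continues: "The duration of the follow-up in days will be summarized", and the listed statistics include the mean, the minimum and the sum in patient-years.
- **Duration on study** runs from the first dose to the last study visit.

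The section has no cap at the last visit or death and no floor at zero. Nothing elsewhere in the SAP or protocol supplies one.

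The protocol leaves several ways for the last visit to fall on, or just after, a dosing day.

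- Section 5.1.1 (Study Period 2): "During Weeks 1 to 8, site personnel will administer IP". In Weeks 9 to 12 participants inject at the site under supervision.
- Section 5.1.1 (Study Period 3): participants who stop treatment and will not return for safety follow-up "will be asked to perform an early termination (ET) visit as their final study visit". No minimum interval after the last dose is given.
- Section 8.3: a participant is lost to follow-up if he or she "repeatedly fails to return for scheduled visits and is unable to be contacted by the study site".

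**The concern.** The LY formula assumes that every participant is seen at least 7 days after the last dose. Where that is false it returns a negative duration. The patient-year sum then subtracts time that other participants did contribute, and the reported minimum is a value that cannot occur.

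The offset applies to LY only, so the distortion falls in the two LY arms and not in the comparator. Follow-up matters more than usual here, because it describes how long participants were observed after stopping a long-acting insulin.

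**Working it through.** **Inputs.** Protocol 10.1: 375 randomized 1:1:1 (250 on LY), 20% dropout, 300 completers. This reproduces: 300 / 0.80 = 375. SAP 4.10.1 states no figure of its own. A completer's last LY dose is at Week 31 (day 217; protocol 7.8.1) and Visit 801 is at Week 37 (day 259). Durations are taken as plain date differences, since the SAP does not say that a day is added.

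**Formulas.** Let F be the first dose, L the last dose, V the last visit, and d = V - L.

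- LY exposure = L + 7 - F
- LY follow-up = V - (L + 7) = d - 7
- Duration on study = V - F
- Hence exposure - duration on study = 7 - d

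For d = 0 to 6, follow-up is -7 to -1 days and exposure runs 7 to 1 days beyond time on study. At d = 7 the durations agree. A death within 6 days of a dose leads to the same place, because no later visit can occur.

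**Individual cases (days, F = 0).** The degludec column applies the degludec rule to the same dates.

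| Case | LY exposure | On study | LY follow-up | After fix | Degludec follow-up |
|---|---|---|---|---|---|
| One dose, no return | 7 | 0 | -7 | 0 | 0 |
| Lost after Week 8 site dose (day 56) | 63 | 56 | -7 | 0 | 0 |
| ET visit 3 days after that dose | 63 | 59 | -4 | 0 | 3 |
| ET visit 7 days after that dose | 63 | 63 | 0 | 0 | 7 |
| Safety visit 42 days after that dose | 63 | 98 | 35 | 35 | 42 |
| Completer (last dose day 217, last visit day 259) | 224 | 259 | 35 | 35 | - |

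**Size.** The documents do not give the share of participants who leave on a dosing day, so a range is shown. Assumptions: affected participants have d = 0 (the worst case); everyone else has 35 days of follow-up; completers have 224 days of exposure and leavers 112.

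| Share of 250 LY | Affected | Days subtracted (7 each) | Patient-years | Share of true follow-up | Share of LY exposure |
|---|---|---|---|---|---|
| 2% | 5 | 35 | 0.10 | 35 / 8,575 = 0.4% | 0.06% |
| 5% | 12.5 | 87.5 | 0.24 | 87.5 / 8,312.5 = 1.1% | 0.16% |
| 10% | 25 | 175 | 0.48 | 175 / 7,875 = 2.2% | 0.33% |
| 20% (ceiling) | 50 | 350 | 0.96 | 350 / 7,000 = 5.0% | 0.69% |

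At the ceiling, mean LY follow-up is (7,000 - 350) / 250 = 26.6 days, against 7,000 / 250 = 28.0.

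The exposure share depends little on the 112-day assumption. With 112 days it is 350 / (200 x 224 + 50 x 112) = 350 / 50,400 = 0.69%. With no other exposure time for leavers it is 350 / 44,800 = 0.78%.

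**The case against.** The strongest reply has three parts.

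1. **The 7 days are deliberate.** They stand for the period that a weekly injection covers. A participant who is injected and then lost was still exposed to the drug that week. This stands. A reader might infer that any LY exposure counted beyond the last contact is an error, but the documents do not support that: the SAP gives drug coverage as its reason, and loss of contact does not end coverage. Exposure is wrong only if it runs past death, or if it is used as time during which events could have been observed.

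2. **No stated comparison uses the follow-up duration.** SAP 4.10.1 only describes it, and adverse events in SAP 4.10.2 are counts and percentages of participants. This also stands. A reader might infer that post-treatment hypoglycemia rates are corrupted, because SAP Table BDCM.1 uses log exposure as the offset and covers the post-treatment period. The table note, however, divides by days at risk, and the SAP does not say that the 4.10.1 follow-up duration is that quantity. The risk is real only if a programmer makes that link; a log of zero or a negative number would then be undefined.

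3. **The 5% figure is a ceiling.** It needs every assumed dropout to leave on a dosing day. The protocol plans visits about 1 and 6 weeks after the last dose for those who stop early (5.1.1), asks them to stay in the trial (8.1.1), and expects diligent contact attempts (8.3). From Week 13, home injection is the default, so a dose and a visit no longer coincide automatically. All of this makes the true number smaller.

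None of these points answers the central one. The rule as written returns a negative duration for a participant the protocol allows to exist.

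**Conclusion.** The point holds as a minor error in a derivation rule. For LY participants whose last visit falls 0 to 6 days after the last dose, follow-up is -7 to -1 days, and those values enter the planned summaries.

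The effect is at most 7 days per affected participant. The number affected is unknown. The ceiling is about 5% of LY follow-up and 0.7% of LY exposure, under the assumptions shown. Participants who attend the visit about 6 weeks after the last dose are unaffected, and so are the primary and secondary efficacy analyses.

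Two conditions apply. The 7-day limit, and the degludec minimum of 0, assume that no home dose is recorded after the last visit. If durations were counted inclusively, each value would rise by one day and the negative range would be -6 to -1.

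**What to change.** Add to SAP 4.10.1:

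- LY follow-up starts at the earliest of last dose + 7 days, last study visit and death, so that it cannot be below 0.
- LY exposure ends at last dose + 7 days or death, whichever comes first.

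Add to SAP Table BDCM.1:

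- State which duration is the offset, or the days at risk, in each period. Where it is exposure or follow-up time, cap it at the last visit or contact.
- State how a participant with zero time in a period is handled, since the log of zero is undefined.

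For affected participants, exposure plus follow-up will then exceed duration on study by up to 7 days; a table footnote should say so. Completers keep 224 and 35 days.

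The cost is a few lines of SAP text and a minimum function in the program, with no new data.

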4.10.2. Adverse Events (AEs)

Adverse events will be summarized as treatment emergent AEs (TEAEs, defined as events that are newly reported after the first dose of study basal insulin or reported to worsen in severity from baseline) for the Safety Population and compared between treatments unless otherwise specified. The Medical Dictionary for Regulatory Activities (MedDRA) Lowest Level Term (LLT) will be used in determination of the treatment-emergent status. The maximum severity for each LLT during the baseline period will be used as baseline severity. All analysis will be performed on the data collected from the date of first dose of study drug to the end of the study (up to Visit 801).

The number and percentage of patients with TEAEs will be summarized by treatment using MedDRA PTs nested within System Organ Class (SOC). Events will be ordered by decreasing frequency within SOC.

The number and percentages of patients with TEAEs ($\geq 2\%$ before rounding) will be summarized by treatment using MedDRA PT (without regard to SOC). Events will be ordered by decreasing frequency.

A TEAE considered possibly related to study drug will be summarized, separately, by treatment group using MedDRA PT nested within SOC. Events will be ordered by decreasing frequency within SOC.

A by-patient listing of all AEs for the Safety Population will be created including, but not limited to, SOC, event PT, severity, and relationship to study drug for all randomized patients.

Discontinuations due to AEs will be summarized by PT and compared between treatment groups using Fisher's exact test for the Safety Population.

Summary of treatment emergent SAEs similar to summaries for the proportion of patients experiencing each reported TEAE by SOC will be included for the Safety Population.

All SAEs (including death) will be listed for the Safety Population.

4.10.3. Adverse Events of Special Interest (AESI)

Summary and analysis of TEAEs related to the following adverse events of special interest (AESIs) is specified in this section:

- deaths and nonfatal cardiovascular events
- hypoglycemia events
- hepatobiliary events
- injection site reactions
- systematic hypersensitivity reactions

4.10.3.1. Death and Nonfatal Cardiovascular Events

Deaths and nonfatal cardiovascular AEs will be adjudicated by an independent Clinical Endpoint Committee. The following events will be adjudicated and listed by patient for all randomized population: death due to cardiovascular events, myocardial infarction (MI), hospitalization for unstable angina, stroke, or transient ischemic attacks (TIA). The actual term and PT of the event, date of first dose and last dose of study drug, result of adjudication, and time from first dose to event will be listed.

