### **3.3. Benefit/Risk Assessment**

The data from the SAD study and the ongoing MAD study (Studies BDCA and BDCB) have shown that LY3209590 was well tolerated and the adverse drug reactions are in line with those reported for long acting insulins.

Potential risks associated with LY3209590, derived from the known risks of long acting insulins are hypoglycemia, hypersensitivity reactions (localized allergy and/or systemic allergy), undesirable effects at the injection site (injection-site reactions and lipodystrophy), and peripheral edema. An additional risk based on preclinical data could be an elevation of liver aminotransferases. To date, this has not been observed in study participants or healthy volunteers exposed to LY3209590 for up to 6 weeks.

More information about the known and expected benefits, risks, Serious Adverse Events (SAE) and reasonably anticipated AEs of LY3209590 are to be found in the Investigator's Brochure.

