#### **9.4. Safety**

##### **9.4.1. Cardiovascular Events**

Deaths and nonfatal CV AEs will be adjudicated by a committee of physicians external to Lilly with cardiology expertise. The nonfatal CV AEs to be adjudicated include: myocardial infarction; hospitalization for unstable angina; hospitalization for heart failure; coronary

interventions (such as coronary artery bypass graft or percutaneous coronary intervention); and cerebrovascular events, including cerebrovascular accident (stroke) and transient ischemic attack.

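### The closed list in SAP 4.10.3.1 omits heart-failure hospitalisation and coronary interventions from the adjudicated-event listing and narrows deaths to cardiovascular ones, contrary to Protocol 9.4.1

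*SAP*

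**What the plan says.** Protocol 9.4.1 opens without any restriction on cause of death: "Deaths and nonfatal CV AEs will be adjudicated by a committee of physicians external to Lilly with cardiology expertise". It then names the nonfatal events in one sentence that runs across a page break: "myocardial infarction; hospitalization for unstable angina; hospitalization for heart failure; coronary" and, continuing, "interventions (such as coronary artery bypass graft or percutaneous coronary intervention); and cerebrovascular events, including cerebrovascular accident (stroke) and transient ischemic attack".

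Protocol 10.3.4.1 commits to a by-participant listing of cardiovascular AEs, both as reported and as adjudicated, with a summary by treatment group if there are enough cases. It does not restrict the listing to particular event types.

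SAP 4.10.3.1 starts in the same general terms: "Deaths and nonfatal cardiovascular AEs will be adjudicated by an independent Clinical Endpoint Committee". The next sentence sets the operative rule: "The following events will be adjudicated and listed by patient for all randomized population: death due to cardiovascular events". The full run of items is "death due to cardiovascular events, myocardial infarction (MI), hospitalization for unstable angina, stroke, or transient ischemic attacks (TIA". For each listed event the SAP then asks for the reported term, the preferred term, the first and last dose dates, the adjudication result and the time from first dose.

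**The concern.** The SAP list is worded as complete. Nothing in it signals that the items are examples, so a programmer building the output would filter on exactly those five items. Two nonfatal event types that the protocol sends to the committee would then have no place in the listing, nor would any death that was not cardiovascular.

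At stake is the reporting of the committee's work. The SAP specifies no other output that carries the adjudication result. A heart-failure hospitalisation or a revascularisation could be sent to the committee and decided there, and the report would show only the investigator's term. For deaths, a reader could not see how the committee classified those it judged non-cardiovascular.

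**Working it through.** No arithmetic beyond counting applies. The check is an item-by-item comparison of Protocol 9.4.1 with the list in SAP 4.10.3.1, followed by a search of the rest of the SAP for the missing items.

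| Event | Protocol 9.4.1 | SAP 4.10.3.1 list |
|---|---|---|
| Cardiovascular death | yes (all deaths) | yes |
| Death from other causes | yes (all deaths) | no |
| Myocardial infarction | yes | yes |
| Hospitalisation for unstable angina | yes | yes |
| Hospitalisation for heart failure | yes | no |
| Coronary interventions | yes | no |
| Stroke | yes | yes |
| Transient ischaemic attack | yes | yes |

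1. **Nonfatal events.** The protocol names six types if stroke and TIA are counted separately. The SAP list has four. The difference is 6 − 4 = 2: heart-failure hospitalisation and coronary interventions. The SAP adds none that the protocol lacks.

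2. **Deaths.** The SAP contradicts itself. Its first sentence adjudicates deaths of any cause, as the protocol does; its list keeps only cardiovascular deaths. The AESI bullet in SAP 4.10.3 is also unrestricted. The narrower item is circular as well if adjudication is what assigns the cause of death, since the cause would then have to be known before the event qualified.

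3. **Rest of the SAP.** Neither heart-failure hospitalisation nor coronary intervention appears elsewhere as an adjudicated or listed event. SAP 4.10 names adjudicated cardiovascular events as a safety measure but does not define them.

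4. **What still reaches the report.** SAP 4.10.2 lists all AEs by patient and all SAEs including death, for the Safety Population. Protocol 9.2.1 makes hospitalisation a criterion for seriousness, so a heart-failure hospitalisation in a dosed participant is in the SAE listing. A coronary intervention is there if it was recorded as an AE or SAE. Neither listing is specified to carry the adjudication result or the time from first dose.

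5. **Stated reason.** SAP 4.10.3.1 gives no reason for the shorter list, and the revision history does not mention it among the main changes.

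**The case against.** The strongest reply is that little is lost. The events appear in the AE and SAE listings whatever SAP 4.10.3.1 says. Adjudication is commissioned by the protocol, not by the SAP, and Protocol 10.3.4.1 still calls for adjudicated cardiovascular AEs to be listed. The SAP's opening sentence is general enough to cover everything the protocol names. SAP 4.1 allows a change of method to be justified in the clinical study report, so silence in the SAP is not in itself a breach. A narrower listing may even be deliberate, because Protocol 10.3.4.6 defines the cardiovascular AESI as major adverse cardiovascular events and does not say which events count.

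Much of this stands, and it rules out several stronger readings that a reader might infer:

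- **That these cases would be missing from the report.** SAP 4.10.2 does not support this. What would be missing is the adjudicated classification and its timing.
- **That the SAP plainly drops non-cardiovascular deaths from adjudication.** The section says both things, so the defect is a contradiction.
- **That the heart-failure omission bears on a known drug risk.** Protocol 3.3 does name "injection-site reactions and lipodystrophy), and peripheral edema" among potential risks carried over from long-acting insulins. Neither document links edema to heart failure or lists heart failure as a potential risk of LY3209590.
- **That each omitted case would change the safety conclusions.** The documents give no expected event count, and this output is a listing with no test or estimate.

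The reply does not remove the mismatch. A general opening sentence does not override a closed operative list directly below it, and the SAP does not say that a narrower listing was intended. Protocol 10.3.4.1 has no output in the SAP that would meet it in full.

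**Conclusion.** The point holds as a mismatch in a descriptive safety listing. SAP 4.10.3.1 leaves out two of the six nonfatal event types in Protocol 9.4.1, and on deaths it contradicts both the protocol and its own first sentence. Followed as written, the adjudication result and the time from first dose would go unreported for these cases, and Protocol 10.3.4.1 would be only partly met.

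This rests on reading the SAP list as closed, which is how it is worded, and on the listing being programmed from it. The primary HbA1c analysis, the error rate, the sample size and the capture of AEs and SAEs are untouched. The number of cases affected cannot be estimated from the documents. The correction is still worth making, because the present rule conflicts with the protocol and costs almost nothing to put right.

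**What to change.** In SAP 4.10.3.1, replace the list with the one in Protocol 9.4.1: add hospitalisation for heart failure and coronary interventions, and replace the cardiovascular-death item with all deaths, showing the adjudicated cause for each. If a narrower listing is intended, say so and give the reason in the SAP or the clinical study report, as SAP 4.1 provides, and state where the remaining adjudication results will be shown.

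The cost is one SAP line and one listing filter. No new data are needed, since the protocol already commits the committee to these adjudications.
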